## 6. STUDY TREATMENT

### 6.1. Investigational Product and Other Study Treatment

The term ‘study treatment’ is used throughout the protocol to describe any combination of products received by the subject as per the protocol design. Study treatment may therefore refer to the individual study treatments or the combination of those study treatments. Study treatment specifically related to sirukumab and matching placebo is distinguished by the use of the terminology “subcutaneously-administered blinded study drug or treatment (sirukumab and matching placebo)”.

Sirukumab and matching placebo will be supplied by the Sponsor. Both sirukumab and matching placebo will be administered subcutaneously using an autoinjector device. The sirukumab drug product provided for this study is supplied in a 1 mL Pre-filled Syringe (PFS) fitted with a spring-powered, disposable autoinjector device for single use SC administration of liquid biologic drug products (SmartJect Autoinjector) that is permanently assembled on the syringe. The sirukumab PFS is aseptically filled to deliver a dose of either 100 mg/1.0 mL or 50 mg/1.0 mL of sirukumab in a Becton-Dickinson (BD) Hypak, 1 mL glass SCF (presiliconized) syringe barrel with a 26 gauge (G) ½ inch fixed needle, an elastomeric needle shield, and a fluoropolymer coated elastomeric plunger stopper. Placebo for sirukumab PFS provided for this study is supplied in a matching presentation.

However, as a contingency, sirukumab may also be supplied as a single-use prefilled syringe-Ultrasafe (PFS-U), which is a ready to use liquid filled 1-mL-long syringe product supplied with a passive safety needle guard (UltraSafe Passive Delivery System, Safety Syringes, Inc.) for SC administration. Placebo for sirukumab PFS-U will also be supplied as appropriate.

The needle shield on the PFS (either assembled into UltraSafe needle guard or autoinjector/prefilled pen) is made with a derivative of natural rubber latex, which may cause allergic reactions in individuals sensitive to latex.

Prednisone for the pre-specified standard blinded taper will be provided by the Sponsor. The prednisone used in the blinded taper of this study is manufactured by Jubilant Cadista (Salisbury, MD) and supplied to the Sponsor by Myoderm (Norristown, PA).

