4.4. Analysis Visits

Data will be presented and analyzed according to the visit recorded in the database. For other efficacy and safety data that visit are entered, no visit windows will be defined as sites should have case report form (eCRF) instructions and training to ensure reasonable data entry. If a visit happens outside the protocol-defined window (Week X \pm 3 days), one of the following will be occur:

- If it is recorded as Week X visit, no visit re-mapping will be done (except for PRO endpoints and Part B visits) and the recorded visit will be used in all analysis.
- If it is recorded as unscheduled visit, it will be treated as unscheduled visit.

In general, only those assessments which are assigned to an analysis visit will be included in the summary tables and figures and will be presented by visit. Unscheduled visits will not be included in summary tables or figures, with the following exceptions: if the table or figure includes data values for all post-baseline assessments (worst/best/maximum/minimum post-baseline assessments), or for tables which report the values during a period of time, unscheduled visits will be included. All unscheduled visits will be included in the listings.

When reporting results or events that are reported on an ongoing basis, such as cumulative prednisone dose or flare at Week X: All results/events will be taken into account that occur inclusively between the day after the Week X-1 visit and the day of the Week X visit. The actual day of the Week X visit will always be taken into account as the day of visit X, even if the actual visit occurred outside of planned visit window.

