4.6. Handling of Missing Data

4.6.1. Treatment Failure Definition

For the primary endpoint derivation, a treatment failure is defined as any subject who:

1. Discontinued permanently SC IP prior to completing week 52 visit due to any reason and continued in the study (i.e. follow-up off treatment)
- or
2. Withdrew from the study for any reason earlier than 10th October 2017, the study termination date.

A subject will be considered a treatment failure from the earliest date that the subject meets any of the 2 treatment failure criteria. Only withdrawals prior to 10th October 2017 will be considered, withdrawals on or after this date will likely be result of study termination at sponsor's request and not provide an accurate summary of treatment response.

A subject that temporarily has their treatment of SC IP put on hold, will not be considered as permanent discontinuations.

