4.6.2. Sustained Remission

4.6.2.1. Main Analysis

The following procedures will be used to handle missing data for derivation of sustained remission (i.e. endpoints mentioned in [Section 8.1](#) and [Section 8.2.2](#)):

1. Any subject who is classified as a treatment failure (as per definition of [Section 4.6.1](#)) will be considered as not achieving sustained remission for the primary efficacy analysis and the supportive analyses of the primary efficacy endpoint.

2. Subjects with all four of the components of the primary endpoint missing at two consecutive scheduled visits will be considered as not achieving sustained remission for these two visits.
3. Subjects with all the components missing at Week X ($X \neq 52$) visit will be considered as achieving sustained remission at Week X visit if achieving sustained remission at the neighboring visits; as not achieving sustained remission otherwise. Data recorded at unscheduled visits will be taken into account based on the unscheduled visit date and will be associated with the next scheduled visit occurring after the unscheduled visit date.
4. Subjects with at least one of the four components of the primary endpoint missing at Week 52 visit will be considered as not achieving sustained remission at Week 52 visit.
5. When only a subset of the components is missing at Week X visit, the rules will be applied to the components first and then the imputed components are used to impute the values at post-baseline values. Similar rules as for complete missing visits are applied:
 - a. Subjects with some components missing at 2 consecutive visits will be considered as not achieving sustained remission for the missing components at these 2 visits.
 - b. Subjects with some components missing at Week X ($X \neq 52$) visit will be considered as achieving sustained remission for the missing components at Week X visit if achieving sustained remission at the neighboring visits; as not achieving sustained remission otherwise
 - c. Subjects with some components missing at the Week 52 visit will be considered as not achieving sustained remission for the missing components at the Week 52 visit.

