If any concomitant corticosteroid medication when the unit is not in (Actuation, Application, Area under curve, Cubic centimeter, Cells, Cells per kilogram, Fingertip unit, Drops, Gum, Inhalation, Kilocalories, Minimum alveolar concentration, Mega becquerels (MBq), Millicurie, Nebule, Patch, Powder, Puff, Ring, Spray, Suppository) or any of concomitant non-corticosteroid medication identified as “GCA related” with the question “Was drug administered as a rescue medication?” is ticked as “Yes” and if the first SC IP Date ≤ Concomitant medication start date ≤ Week 52 visit date, then subject will fail the criterion.

If all of the 4 criteria are met, subject will be considered in sustained remission at Week 52. If 1 of the 4 criteria is not met, the subject will be considered as not in sustained remission at Week 52.

For more details on imputation of missing data for the primary endpoint, please refer to [Section 4.6.2.1](#).

Given study termination, only the subset of subjects who attended the Week 52 visit or who discontinued study treatment or withdrew from study prior to the 10th of October 2017 will be included in this analysis.

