If any concomitant corticosteroid medication when the unit is not in (Actuation, Application, Area under curve, Cubic centimeter, Cells, Cells per kilogram, Fingertip unit, Drops, Gum, Inhalation, Kilocalories, Minimum alveolar concentration, Mega becquerels (MBq), Millicurie, Nebule, Patch, Powder, Puff, Ring, Spray, suppository) or any of concomitant non-corticosteroid medication identified as “GCA related” with the question “Was drug administered as a rescue medication?” is ticked as “Yes” and if the first SC IP date \leq Concomitant medication start date \leq Week X visit date, then the subject will fail the criterion.

Please note that once a subject fails a criterion, he/she will also fail all future criteria from subsequent visits.

For more details on imputation of missing data for sustained remission endpoint, please refer to [Section 4.8.2.1](#).

If all of the 4 items are met and the subject did not discontinue SC IP before the Week X visit date, the subject will be considered in sustained remission at Week X. If 1 of the 4 items is not met or if the subject discontinued SC IP before the Week X visit, the subject will be considered as not in sustained remission at Week X.

Given study termination, only the subset of subjects who attended the Week X visit or who discontinued study treatment or withdrew from study prior to the 10th of October 2017 will be included in this analysis.

Number of subjects who flared and subjects who did not complete the prednisone blinded taper will also be summarized over time on the ITT Set.

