9.1. Adverse Events

The definition of an AE is detailed in Section 12.4.1 in Appendix 4 of the protocol.

Treatment-emergent AEs:

A treatment-emergent AE for Part A is defined as an AE with a start date during the exposed period.

The exposed period is defined as the period from the 1st dose of SC IP to:

- Early withdrawal: last dose of SC IP + 16 weeks

- Completers (subjects who attended the week 52 visit):
 - Week 52 visit if entering into part B
 - Last dose of SC IP + 16 weeks if not entering into part B

Unless otherwise specified, AE outputs will be based on TEAEs.

All AEs will be coded by system organ class (SOC) and preferred term (PT) according to the Medical Dictionary for Regulatory Activities (MedDRA, Version 19.0 or higher).

An overview summary of TEAEs, including counts and percentages of subjects will be generated by actual treatment group, with any of the following categories:

- Any TEAE, TEAEs related to study treatment (SC IP and/or prednisone study drug), TEAEs leading to permanent discontinuation of study treatment, TEAEs leading to dose interruption/delay, TEAEs leading to dose reduction, TEAEs leading to dose increase, TEAEs leading to dose not changed.
- Any serious TEAEs, serious TEAEs related to study treatment (SC IP and/or prednisone study drug), fatal serious TEAEs, and fatal serious TEAEs related to study treatment.
- Any TEAE of special interest (TEAESI) (see [section 9.1.8](#) for further details), TEAESIs related to study treatments (SC IP and/or prednisone study drug), TEAESIs leading to permanent discontinuation of study treatment, TEAESIs leading to dose reduction, TEAESIs leading to dose increase, TEAESIs leading to dose not changed, TEAESIs leading to dose interruption/delay.

A listing presenting the relationship between SOC, PT, and AE reported will be provided.

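### After termination, subjects first dosed too late for a visit enter the sustained-remission proportion essentially only as failures, which biases it downward in any arm with a late stopper

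*SAP*

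**What the plan says.** The study was terminated on 10 October 2017, and early withdrawal visits were completed by 30 November 2017 (SAP 1.1). Efficacy is reported by summary statistics only (SAP 1.1 and 8).

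- **Who is counted.** At Week 52, SAP 8.1 includes "only the subset of subjects who attended the Week 52 visit or who discontinued study treatment or withdrew from study" before 10 October 2017. SAP 8.2.2 uses the same rule at every visit from Week 12: "only the subset of subjects who attended the Week X visit or who discontinued study treatment or withdrew from study" before that date. SAP 11.4.1 repeats it for Part B.
- **How they are scored.** SAP 4.6.1 defines a treatment failure as a subject who "Discontinued permanently SC IP prior to completing week 52 visit due to any reason and continued in the study", or who withdrew before 10 October 2017. Under SAP 4.6.2.1 such a subject "will be considered as not achieving sustained remission for the primary efficacy analysis and the supportive analyses of the primary efficacy endpoint". SAP 8.2.2 adds that "if the subject discontinued SC IP before the Week X visit, the subject will be considered as not in sustained remission at Week X".
- **Termination withdrawals.** SAP 4.6.1 does not count withdrawals on or after 10 October 2017 as failures, because they would not describe treatment response accurately. The discontinuation item in the same list carries no date.
- **Terms.** The counting rule speaks of study treatment, which Protocol 6.1 uses "to describe any combination of products received by the subject as per the protocol design", prednisone included. The scoring rule refers to the subcutaneous product (SC IP) only.

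**The concern.** For a subject who could not reach Week 52 before the study closed, the only practical way into the table is to stop or withdraw, and that is always scored as a failure. A subject first dosed on the same day and still on SC IP at termination is not counted. Inclusion therefore depends on outcome for late entrants, but not for early ones.

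At stake is the tabulated primary endpoint by arm. SAP 1.1 and 8.1 disclose the termination and the subset, but do not say that the subset pushes the proportion in one direction.

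**Working it through.** **Plan's own figure.** The SAP gives no figure for the post-termination proportion. The only computable figure attached to the planning rates (SAP 4.1: 70% vs 30%, 51 vs 34 subjects, two-sided 5%) is 96% power. A pooled normal approximation gives 96.5%, so it reproduces. Those two rates are used below as examples.

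**Dates.** Week 52 is day 364 after first dose, with a ±3-day window.
- The last first-dose date whose full window closes by termination is 10 Oct 2017 − 367 days = 8 Oct 2016.
- The last first-dose date whose window opens by 30 Nov 2017 is 30 Nov 2017 − 361 days = 4 Dec 2016.
- Subjects first dosed from 9 Oct to early Dec 2016 might therefore still have attended Week 52. Later subjects could not have attended in window.

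**Direction.** Subjects first dosed by 8 Oct 2016 essentially all either attended Week 52 or stopped before it. With stable case mix, that group alone estimates the true rate *p*. Late stoppers add to the denominator and nothing to the numerator, so they can only lower the result.

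**Size (illustrative).** All of these are assumptions, because the documents give neither accrual nor stopping rates:
- *F* is the share of subjects with at least 52 weeks of potential follow-up.
- The others are uniform over 0–52 weeks.
- SC IP stopping has a constant hazard with annual probability *d*, where *d* ≤ 1 − *p* because every stop is a failure.

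With L = −ln(1 − d), the expected share of late subjects who have stopped is a = 1 − (1 − e^(−L))/L = 1 − d/L. This is 0.0509 at d = 10% and 0.1037 at d = 20%. Then

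reported = F·p / [F + (1 − F)·a].

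Example, F = 25%, p = 70%, d = 10%: 0.175 / (0.25 + 0.75 × 0.0509) = 0.175 / 0.288 = 60.7%.

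| F | factor, d = 10 / 20% | true 70% shows as | true 30% shows as | both arms truly 50%, d = 10% vs 20% |
|---|---|---|---|---|
| 25% | 0.87 / 0.76 | 60.7 / 53.4% | 26.0 / 22.9% | 43.4 vs 38.1% |
| 50% | 0.95 / 0.91 | 66.6 / 63.4% | 28.5 / 27.2% | 47.6 vs 45.3% |
| 75% | 0.98 / 0.97 | 68.8 / 67.7% | 29.5 / 29.0% | 49.2 vs 48.3% |

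At F = 25%, per 100 subjects, 75 × a = about 4 to 8 late subjects enter, all as failures. The other 71 to 67 late subjects, still on SC IP, are left out.

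**Check.** Simulation (4 million subjects, on-treatment failure allowed) gives 60.7% and 53.4% for p = 70%, F = 25%, d = 10% and 20%. The denominator proposed below returns 70.0% in both.

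**Earlier visits.** With F_X = F + (1 − F)(52 − X)/52 and L scaled by X/52, the factors at F = 25% for d = 30% to 10% are 0.75–0.90 at Week 48, 0.81–0.93 at Week 44, 0.89–0.96 at Week 36 and 0.96–0.99 at Week 24. The effect sits mainly at late visits.

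**The case against.** **Some late subjects may have attended.** SAP 8.1 most naturally attaches the 10 October date to stopping or withdrawing, not to attending. A reader might infer that anyone enrolled under Amendment 3 (17 November 2016) could appear only as a failure. The documents do not support that. A first dose on that date gives a Week 52 window opening on 13 November 2017 (17 Nov 2016 + 361 days), 17 days before 30 November. How many such visits took place is not stated. This stands, and is why the claim says essentially.

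**Not every arm need be affected.** An arm with no late stopper has no such bias. At F = 25% and d = 10%, an arm of the planned 34 subjects would have none with probability (1 − 0.0382)^34 = about 27%. This stands.

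**Late failures are dropped too.** Late subjects who flared or were rescued but stayed on SC IP are also left out, so those left out are not all responders. This is true, but it does not reverse the direction, because the early group is already complete without them.

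**No ceiling can be stated.** A reader might take the case where every failure enters as an upper limit on the bias. With a constant hazard, a true 70% then shows as 47/60/67% at F = 25/50/75%. If failures come early it shows as 37/54/64%, so the former are constant-hazard values and not a bound.

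**Other outputs help.** Efficacy is descriptive. Failures are categorised and listed (SAP 8.1.1), flares and taper non-completion are summarised on the ITT set (8.2.2), and a Kaplan-Meier analysis of first flare is planned (8.2.3.1). This limits the harm, but none of it corrects the primary proportion.

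**Conclusion.** The denominator rule in SAP 8.1, 8.2.2 and 11.4.1 is wrong as written and should be fixed. Confidence in the mechanism and direction is high, given similar response rates in early and late enrolees. Amendment 3 changed eligibility, including prior anti-IL-6 use (Protocol, Revision Chronology), so that assumption is not secure. Even without it, late stoppers can only pull the figure below the early group's own proportion.

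Confidence in the size is low. Under the stated assumptions, the loss from a true 70% runs from 1 to 2 points (F = 75%) to 9 to 17 points (F = 25%) at 10–20% annual stopping. SAP 1.1 describes the number completing Week 52 as limited, so a low F is plausible but not established. A contrast between arms shrinks if late stopping is similar, and can move either way if it is not. No hypothesis test is affected.

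**What to change.** In SAP 8.1, 8.2.2 and 11.4.1, replace the subset sentence with a denominator defined by potential follow-up: all subjects in the relevant set whose scheduled visit plus its window falls on or before 10 October 2017, whatever their status.

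- **Part A:** the ITT set, with first SC IP dose by 8 Oct 2016 for Week 52, 5 Nov 2016 for Week 48 and 3 Dec 2016 for Week 44 (10 Oct 2017 minus 367, 339 and 311 days).
- **Part B:** subjects in sustained remission at Week 52 who entered Part B, with that part's own visit window.
- **Delayed visits:** use the date only to set eligibility. An eligible subject's slightly late visit still counts, in line with SAP 4.4: "If it is recorded as Week X visit, no visit re-mapping will be done".
- **SAP 4.6.1 item 1:** add the same 10 October 2017 date, so that an SC IP stop caused by termination is not scored as a failure for an eligible subject whose visit was slightly late.
- **Footnote per arm:** the number left out, including any who attended the visit after 10 October 2017, with their outcomes.

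The replacement also removes the mismatch between study treatment and SC IP in those sections, so no separate edit is needed there.

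The cost is SAP wording and modest reprogramming, with no new data. The downsides are fewer subjects, possible loss of some observed late Week 52 outcomes (responders included), and a Week 52 set that pre-dates Amendment 3, the last eligible first dose being 40 days before it.

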8.1.1. Primary Analysis

The proportion of subjects in sustained remission at the Week 52 visit will be summarized by treatment group. Subjects not in sustained remission will be categorized by the criterion they failed to achieve. A listing will be produced with the detail of each criteria met or not met over time. A listing of clinical assessment of GCA will be produced over time.

8.2. Secondary Efficacy Endpoints

8.2.1. Cumulative Prednisone Dose (Study Drug and Corticosteroid Rescue Therapy) over Time

Cumulative prednisone is the cumulative prednisone dose from the taper (both open-label and blinded) as well as from the corticosteroid rescue therapies, as defined in [Section 3.3](#) and [Section 7.3](#). Cumulative dose at Week X will be derived as the sum of all the doses from baseline to Week X. If a subject withdraw from study between two scheduled visits, all prednisone doses recorded between his last scheduled visit and study withdrawal will be associated to the next scheduled visit. For example, if a subject withdraw between the Week 24 visit and the Week 28 visit, all doses recorded after the day of Week 24 will be associated to Week 28. For more details on imputation of missing data for the key secondary endpoint, please refer to [Section 4.6.3.1](#).

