#### **5.4.2. Discontinuation of Study Drug**

Permanent discontinuation of study drug will not require the subject to be withdrawn from the study. Subjects should continue where possible to be followed and disease status assessed. Upon permanent discontinuation of subcutaneously-administered blinded sirukumab or matching placebo, corticosteroid dose and treatment will be at the discretion of the investigator.

Study drug (subcutaneously-administered blinded sirukumab or matching placebo) must be permanently discontinued for any of the following:

1. The investigator (in consultation with the medical monitor) believes that for safety reasons (e.g., adverse event) it is in the best interest of the subject to stop treatment.
2. Severe allergic reaction or anaphylactic reaction resulting in bronchospasm with wheezing, or dyspnea requiring ventilatory support, or symptomatic hypotension with a > 40 mmHg decrease in systolic blood pressure that occurs following study drug administration.
3. Reaction suggestive of serum sickness occurring 1-14 days after study drug administration. These may be manifested by symptoms of myalgias, arthralgias, fever, rash, pruritus, facial, hand, or lip edema, dysphagia, urticaria, sore throat, and/or headache.

4. Adverse events (AEs) or laboratory abnormalities indicative of safety concerns which are significant enough to discontinue study drug in the opinion of the investigator.
5. Pregnancy.
6. Liver function abnormalities as specified in Section 5.4.3.
7. Opportunistic infection, ie, an infection by an organism that usually causes disease only in a host whose resistance is lowered (eg, Pneumocystis jirovecii, coccidioidomycosis, Mycobacterium avium).
8. Active or latent TB.
9. Malignancy, excluding nonmelanoma skin cancer.
10. Demyelination, either central or peripheral.
11. Two confirmed consecutive absolute neutrophil counts of  $<0.5 \times 10^9$  cells/L.
12. Two confirmed consecutive platelet counts  $<50 \times 10^9$  cells/L.
13. Acute diverticulitis requiring antibiotic treatment.
14. Gastrointestinal perforation.

Subjects must **not** receive blinded subcutaneous sirukumab or matching placebo during the course of a serious infection. Subjects who temporarily discontinue blinded sirukumab or matching placebo due to an infection or other reasons should continue to follow the prednisone taper schedule.

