4.6.3. Cumulative Prednisone Dose over Time

4.6.3.1. Main Analysis

For the main analysis of cumulative prednisone dose over time (mentioned in [Section 8.2.1](#)), data from subjects who permanently discontinue SC IP prior to completing week 52 visit due to any reason and continue in the study will be used for the analysis. Cumulative prednisone dose will be set to missing once a subject withdraws from the study.

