7.3. Prednisone Intake as a Concomitant Medication

All corticosteroid dosages recorded on the Concomitant Medications - Corticosteroids page in the eCRF will be converted to a prednisone-equivalent average daily dose (mg/day) using a conversion factor for each particular medication. The list will be updated throughout the course of the study to include all corticosteroids taken by the subjects and will be finalized prior to the database lock and unblinding. The conversions of all corticosteroids will be done based on standardized medication name and using the following information from online calculator <http://www.globalrph.com/corticocalc.htm>, retrieved on 24th January 2018

Concomitant Medications with Standardized Medication Name Including the Following Term	Conversion factor for Prednisone - Equivalent Dose (mg)
Cortisone	0,2
Hydrocortisone	0,25
Prednisone	1
Prednisolone	1
Triamcinolone	1,25
Methylprednisolone	1,25
Dexamethasone	6,67
Betamethasone	8,33

Only medications with a unit reported in ‘mg’ will be converted to prednisone.

DOSE2 (prednisone-equivalent dose in mg) = DOSE (collected dose in mg) x conversion factor

DD (daily dose in mg/day) = DOSE2 (prednisone-equivalent dose in mg) x frequency factor

The records from concomitant medication datasets will be mapped to weeks corresponding to the prednisone schedule, e.g. if a subject has prednisone as rescue therapy for 10 days, the first 6 days may be mapped to Week X and the rest of the 4 days will be mapped to Week (X + 1) based on the start and end dates of the rescue medication, as well as the start and end dates of the prednisone tapering schedule at each week.

The following information on corticosteroids taken will be presented in a listing:

- Start and stop dates
- Original units, frequency and dose
- Prednisone-equivalent daily dose (in mg)
- Whether or not it was taken as a rescue medication

- Reason for medication (as collected on the Concomitant Medication-Corticosteroid eCRF page).

Two categories of concomitant prednisone intake will be identified:

- Concomitant prednisone intake as rescue therapy: all concomitant intake of corticosteroids reported for which the question “Was drug administered as a rescue medication?” is “Yes”
- Concomitant prednisone intake for non-GCA-related reasons: all concomitant intake of corticosteroids reported for which the question “Non Giant Cell Arteritis (GCA) related” is ticked

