Summary statistics of cumulative prednisone intake including both taper and rescue medication will be summarized by treatment group and visit as well as overall.

Further discussions regarding the statistical analysis of cumulative prednisone intake including both taper and rescue medication is presented in [Section 8.2.1](#).

Frequencies are free text variables and need to be converted to numerical values. The following free text frequencies will be derived as follows:

Text	Frequency used for conversion
1 OF THE 3 DAYS	1/3
2 OF THE 3 DAYS	2/3
BID	2
DAIL	1
DAILY FOR 2 WEEKS	1
DQ	1
EVERY OTHER DAY	1/2
EVERY 12 HOURS	2
EVERY 2 OF 3 DAYS	2/3
EVERY 2 OF THE 3 DAY	2/3
EVERY 2 OF THE 3DAYS	2/3
EVERY 3TH DAY	1/3
EVERY TWO DAYS	1/2
EVERYDAY	1
EVRY DAY	1
MANE	1
ONCE	1
ONCE DAY	1
ONCE A DAY	1
ONCE D AY	1
ONCE EVERY DAY	1
ONCE OVER A DAY	1
ONCE THE DAY	1
ONCE/DAY	1
ONVE A DAY	1
Q3D	1/3
Q8H	3
QD	1
QOD	1/2
TID	3

8. Efficacy Analysis

All efficacy analyses will be based on the ITT set defined in [Section 4.4.3](#), unless otherwise specified. Subjects will be analyzed according to the treatment groups that they were randomized to, regardless of the treatments they actually received.

Only summary statistics will be produced given study termination.

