11.4.2. Endpoints from Part A Reported during Part B

The following efficacy endpoints will be summarized and listed for Part B as for Part A using the by-line as specified in [Section 11](#), unless otherwise specified. The visit displayed in the outputs will be the re-mapped visit as specified in [Section 11.5](#).

- Cumulative prednisone dose over time:
Derivation will be the same as for Part A, as described in [Section 8.2.1](#). Only corticosteroid rescue therapies, as defined in [Section 3.3](#) and [Section 7.3](#) will be taken into account in the derivation of cumulative prednisone dose over time. All medication taken the day after the Week 52 visit of Part A will be considered in the analysis.
An additional summary will be displayed taking into account prednisone dose taken during both Part A and Part B.
- Number of disease flares per subject over time:

Derivation will be the same as for Part A, as described in [Section 8.2.4](#). All events occurring the day after the Week 52 visit of Part A will be considered in the analysis. The summary table will not use the Part B by-line.

An additional summary will be displayed taking into account all flares occurring during both Part A and Part B.

- Proportion of subjects requiring hospitalizations for disease flare and number of hospitalizations for disease flare over time:
Derivation will be the same as for Part A, as described in [Section 8.2.5](#). All events occurring the day after the Week 52 visit of Part A will be considered in the analysis. The summary table will not use the Part B by-line
- Patient-reported outcomes including SF-36v2 acute, EQ-5D (5L), FACIT-Fatigue, Pain NRS, Steroid Impact Questionnaire, HAQ-DI, PtGA and PhGA are exploratory endpoints in Part B and will only be listed

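### Cumulative prednisone leaves out investigator-directed GCA steroid unless it is ticked as rescue, and no rule says when it must be ticked

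*SAP*

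**What the plan says.** **Definition in Part A.** SAP 8.2.1 states: "Cumulative prednisone is the cumulative prednisone dose from the taper (both open-label and blinded) as well as from the corticosteroid rescue therapies". It refers to SAP 3.3 and 7.3 for what rescue means. SAP 7.3 repeats the scope: "Summary statistics of cumulative prednisone intake including both taper and rescue medication will be summarized by treatment group and visit as well as overall".

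**Categories of concomitant steroid.** SAP 7.3 recognises two. The first is "Concomitant prednisone intake as rescue therapy: all concomitant intake of corticosteroids reported for which the question" about rescue use is answered Yes. The second is "Concomitant prednisone intake for non-GCA-related reasons: all concomitant intake of corticosteroids reported for which the question" about a non-GCA reason is ticked. SAP 3.3 uses the same rescue question and removes non-systemic forms through a list of excluded units.

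**Steroid after the SC drug is stopped.** Protocol 5.4.2 says that upon permanent discontinuation "corticosteroid dose and treatment will be at the discretion of the investigator". SAP 4.6.3.1 uses "data from subjects who permanently discontinue SC IP prior to completing week 52 visit due to any reason and continue in the study", and sets the dose to missing only at study withdrawal.

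**Part B.** Protocol 4.2.2 places corticosteroid use and dose changes at the investigator's discretion. SAP 11.4.2 restricts the Part B sum: "Only corticosteroid rescue therapies" are taken into account.

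**Data available.** SAP 7.3 says "All corticosteroid dosages recorded on the Concomitant Medications - Corticosteroids page in the eCRF will be converted to a prednisone-equivalent average daily dose", limited to records in mg. The records are listed with dates, reason and rescue status.

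**The concern.** The two categories in SAP 7.3 do not cover every case. Steroid given for GCA but not ticked rescue belongs to neither, and it does not enter the sum. The protocol creates a setting for such steroid in Part A by handing steroid decisions to the investigator after a permanent SC stop, without calling that treatment rescue. In Part B there is no study taper, so ongoing prednisone counts only if someone ticked the rescue box.

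A subject in this position is not missing. The derived total stays flat while steroid is still being taken, and a reader of the table cannot see that. Protocol 9.3.3 makes cumulative prednisone at Week 52 the key secondary endpoint, and Protocol Section 3 makes long-term cumulative prednisone a Part B objective with no restriction to rescue. With formal testing dropped, these summaries are what remains to describe steroid sparing, so the label and the content should agree.

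**Working it through.** The documents state no expected total, SD or power for cumulative prednisone, so there is no plan figure to reproduce. The check has two parts: trace the rule, then size what it can leave out.

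**1. What enters the total**

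| Steroid source | Recorded on | Counted? |
|---|---|---|
| Taper, including taper continued after the SC drug is stopped | Taper pages (SAP 3.3) | Yes, Part A |
| Concomitant systemic steroid, rescue Yes | Corticosteroids page | Yes, Parts A and B |
| Concomitant systemic steroid for GCA, rescue not ticked | Corticosteroids page | No; no category in SAP 7.3 |
| Concomitant systemic steroid, non-GCA, rescue not ticked | Corticosteroids page | No |

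The third row is the gap.

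**2. Taper reference, 6-month schedule, 40 mg start (SAP Table 3, 7 days per step)**

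- Open-label weeks: 40 + 35 + 30 + 25 + 20 = 150; 150 × 7 = 1,050 mg.
- Blinded weeks: 15 + 13 + 12 + 10 + 9 + 8 + 7 + 6 + 6 + 5 + 5 + 4 + 4 + 3 + 3 + 2 + 2 + 1 + 1 = 116; 116 × 7 = 812 mg.
- Whole taper: 1,050 + 812 = 1,862 mg.
- First 12 weeks (five open-label, seven blinded): (150 + 74) × 7 = 1,568 mg.

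**3. Illustration in Part A**

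Assume the subject stops both the SC drug and the taper at Week 12, stays in the study, and takes a constant GCA-related dose to Week 52 that is not ticked rescue. The period is 40 × 7 = 280 days. The documents give no such dose; the values below only show a range.

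| Assumed mg/day | Omitted (mg) | Derived total (mg) | Full total (mg) | Share omitted |
|---|---|---|---|---|
| 5 | 1,400 | 1,568 | 2,968 | 47% |
| 10 | 2,800 | 1,568 | 4,368 | 64% |
| 15 | 4,200 | 1,568 | 5,768 | 73% |

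A later stop shrinks the omission: at Week 20, 10 mg/day omits 10 × 224 = 2,240 mg. If the same course is ticked rescue, the omission is 0 mg in every row.

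**4. Illustration in Part B**

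Unticked 5, 10 or 20 mg/day (assumed) omits 840, 1,680 or 3,360 mg by Week 24 (168 days), and 1,820, 3,640 or 7,280 mg by Week 52 (364 days).

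**The case against.** The strongest reply is that the gap is narrower than the definition suggests, and much of that reply stands.

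- Nothing is lost from the database. The steroid is recorded, listed and, when in mg, converted; if ticked rescue, it counts in full.
- Protocol 4.2.1 and 6.3 already give the name rescue to steroid used when a subject cannot follow the taper because of flare, adrenal insufficiency or safety reasons. Many departures after an adverse event may be ticked on that basis.
- Stopping the SC drug does not by itself end the taper. SAP 5.1 has a row for subjects who stop SC drug and complete prednisone, and those doses count. After a temporary stop, Protocol 5.4.2 keeps the subject on the taper.
- A 10 mg/day course held for 40 weeks with no rescue tick is a constructed case. In the example, the assigned dose in the week before Week 12 is 7 mg/day and falling.
- SAP 1.1 and Section 8 limit efficacy output to summary statistics, and few subjects reached Week 52. SAP Section 11 also says that Part B displays only demographics, baseline and safety, so the Part B summary in 11.4.2 may not be produced.
- Leaving non-GCA steroid out of a GCA steroid-sparing measure is a defensible choice, and the endpoint title declares its components.

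What survives is that the total turns on a tick for which the documents give no rule in exactly the two settings where the protocol leaves steroid to the investigator. The planned study-drug and rescue rows do not reveal what is missing.

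**Conclusion.** The concern holds in limited form, at moderate severity. Followed as written, the SAP can understate cumulative prednisone for subjects who stay in the study after permanent SC discontinuation, and for subjects in Part B. In the assumed Part A cases above, the omission is between 0 mg (ticked) and 4,200 mg (unticked, 15 mg/day from Week 12). This rests on the protocol and SAP alone; eCRF completion instructions, which are not in these documents, might settle how the tick is used.

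Three stronger readings are tempting and are not supported.

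- A reader might infer that all such steroid is set to zero. It is zero only when not ticked rescue.
- A reader might infer that the undercount favours sirukumab, because several mandatory SC stopping rules in Protocol 5.4.2 match sirukumab's listed risks in Protocol 4.6.1. The documents give no discontinuation rates or off-drug steroid doses by arm. In Part B the undercount could run the other way if placebo subjects had more active disease. The size and direction of any between-arm bias are unknown.
- A reader might infer that the key secondary test is compromised. No test will be run after termination; only descriptive tables are affected.

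**What to change.** In SAP 8.2.1, 7.3 and 11.4.2, define total cumulative prednisone as the taper dose (Part A) plus every systemic corticosteroid on the Corticosteroids page that is not marked non-GCA-related, in prednisone equivalents and whatever the rescue tick. The unit exclusions in SAP 3.3 can serve to define systemic. Apply the same rule in Part B from the day after the Week 52 visit.

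Keep the planned study-drug and rescue rows. Add a row for other GCA-related steroid, and show non-GCA systemic steroid as a separate row outside the headline total.

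Reconcile SAP Section 11, which limits Part B displays to demographics, baseline and safety, with 11.4.2, which summarises Part B cumulative prednisone.

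The cost is SAP wording and one or two table rows. The records are already collected, and those in mg are already converted. Reported totals may look less favourable.
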